11.4 Analysis of secondary objectives

11.4.1 Number of GCs per unit area in lymph nodes will be quantified ordinally only, in mutually exclusive ordered groups of high, moderate, low, or absent. We will examine association between treatment arm and rank order of number of GCs in contingency table analysis using methods that incorporate the ordinal ranking of one of the variables. We will also model the outcome of rank order of number of GCs as a function of treatment arm, age, and stage using ordinal logistic regression. As above we will first examine whether there is a significant

interaction between stage and treatment arm with respect to the outcome, and if so will present findings stratified by stage.

11.4.2 Presence/absence of necrosis will be analyzed in a similar manner as the dichotomous outcome of presence/absence of GCs, described above under 11.3.1.

11.4.3 Overall survival will be estimated in treatment and control groups using standard Kaplan-Meier life table analyses and will also be evaluated in the multivariable setting using Cox proportional hazards modeling, where covariates of age and stage will be included. As described above we will first examine whether the statistical interaction between stage and treatment arm is significant.

11.5 Analysis of Exploratory Objective

Analyses of changes in lymphocytes will be exploratory in nature. Changes in T regulatory cell concentrations and MDSCs will be assessed in each arm ([name]). These measures will be compared longitudinally between groups using a mixed models approach with subjects being considered as random effects and time and treatment and time by treatment interaction considered as fixed effects. For these analyses the baseline (pre-treatment) assessment of each outcome will be included as a covariate in the mixed model.

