5.3 Exploratory Outcomes

5.3.1 Immunophenotypic changes among monocytes including quantification of MDSCs in pre- and post-treatment blood and tissue samples. Peripheral blood samples at 2 time points (before treatment, and after treatment). Treatment Plan

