5.3 Study-Related Interventions

	Pre-Study ^a	After completion of Vitamin A	Post-Operative
Informed consent	X		
Demographics	X		
Medical history	X		
Concurrent meds	X		
Physical exam	X		
Vital signs	X	X	
Performance Status	X		
B-HCG ^d	X		
Adverse event evaluation		X	X
Research Blood Draw ^e	X	X	
GC Measurement			X

a: Pre-study requirements listed in table must be completed **within** 28 days prior to registration. The research blood draw should be collected **prior** to starting Vitamin A.
b: Additional monitoring interventions may be done per the treating physician depending on which treatment is being given post-assignment.
c: Alkaline phosphatase, total bilirubin, BUN, calcium, creatinine, SGOT[AST], SGPT[ALT]
d: Serum pregnancy test (women of childbearing potential).
e: This procedure is only applicable for patients who chose to participate in the research blood draw

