11.2 Method of Randomization

Patients will be randomized in a 1:1 ratio to receive the vitamin A treatment intervention or standard of care. Patients will be stratified for randomization based on pre-operative stage (stage 1, 2, or 3).

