11.3 Analysis of Primary Objective

11.3.1 The outcome for our primary objective is dichotomous—GCs present/absent. Following basic bivariate analysis in contingency tables of presence/absence by treatment arm we will model presence/absence of GCs in a logistic regression model as a function of treatment arm, stage, and age at diagnosis. We will first examine the statistical interaction term between stage and treatment arm, and if it is significant, we will present findings stratified by stage. If it is not significant, we will remove the interaction term from the final model and include stage as a simple covariate only.

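### Section 11.5 omits pre-operative stage, the only stratification factor; if stage predicts the biomarkers beyond baseline, the reported standard errors will be conservative

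*Combined protocol and SAP*

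**What the plan says.** Section 11.2 sets a 1:1 allocation and one stratification factor: "Patients will be stratified for randomization based on pre-operative stage (stage 1, 2, or 3").

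The models in 11.3 and 11.4 use stage. The primary analysis is a "logistic regression model as a function of treatment arm, stage, and age at diagnosis". Lymph-node germinal centers are modelled "as a function of treatment arm, age, and stage using ordinal logistic regression". Necrosis (11.4.2) follows the primary model, and the Cox model for survival (11.4.3) has age and stage as covariates. In each case a stage-by-arm interaction is examined first.

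Section 11.5 describes the exploratory mixed model as having "subjects being considered as random effects and time and treatment and time by treatment interaction considered as fixed effects", and adds that "the baseline (pre-treatment) assessment of each outcome will be included as a covariate in the mixed model". It names neither stage nor age.

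The data for 11.5 are one blood sample before and one after treatment (5.3 Exploratory Outcomes). Blood is taken from volunteers only: "This procedure is only applicable for patients who chose to participate in the research blood draw" (5.3 Study-Related Interventions, footnote e).

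**The concern.** A factor that restricts the randomization normally belongs in the analysis model. Stratification balances stage between arms, so stage contributes little to the true sampling variation of the arm difference. A model without stage still counts any stage-related spread as residual noise. Its standard error is then larger than the estimate deserves, its intervals are too wide, and a real biomarker difference is a little harder to see. The omission also sets 11.5 apart from the plan's other models without explanation.

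The optional blood draw adds a second, smaller issue. Stratification balances stage among everyone randomized. Among those who also give blood the balance is only approximate, so a chance stage difference between donor arms can add some real variability to an estimate that is not adjusted for stage.

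**Working it through.** **The plan's own figure.** Section 11.5 gives no power, standard deviation or effect size. The only power figure is the 80% in 11.1 for the primary endpoint. A normal approximation for 35% against 53%, 90 per arm, one-sided 0.05, gives 78.8%, close to what is stated. It does not bear on this point.

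**Terms named in each model.**

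| Model | Stage | Age | Baseline value |
|---|---|---|---|
| GC in tumor, logistic (11.3.1) | yes | yes | – |
| GC in nodes, ordinal (11.4.1) | yes | yes | – |
| Necrosis, as 11.3.1 (11.4.2) | yes | yes | – |
| Survival, Cox (11.4.3) | yes | yes | – |
| Treg/MDSC, mixed (11.5) | no | no | yes |

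**Which comparison is affected.** With two samples per patient, 11.5 can be read in two ways.

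- *Baseline as covariate, post-treatment value as outcome.* This is an analysis of covariance, and omitting stage can matter.
- *Both time points as outcomes, no baseline covariate.* The time-by-treatment contrast is within-patient. A stage main effect is constant within a patient and drops out. In simulated fits, the standard error of this contrast was 0.1644 with and without stage when stage had no effect, and 0.1514 with and without stage when stage drove the change.

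**Formula for the first reading.** Let R² be the share of post-treatment variance left after baseline that stage explains. With stage balanced between arms and degrees of freedom ignored:

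reported SE without stage ÷ SE with stage = 1/√(1 − R²)

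| R² (assumed) | Calculation | Excess |
|---|---|---|
| 0% | 1/√1.00 = 1.000 | 0% |
| 1% | 1/√0.99 = 1.005 | 0.5% |
| 5% | 1/√0.95 = 1.026 | 2.6% |
| 10% | 1/√0.90 = 1.054 | 5.4% |
| 15% | 1/√0.85 = 1.085 | 8.5% |

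**Reported against true precision, stage balanced.** Simulated analysis of covariance with 180 patients, stage mix 60/25/15% and within-patient correlation 0.5 (all assumed for the blood analysis). Stage effects are in outcome SDs per stage step.

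| Stage effect | Reported SE without / with stage | Ratio | True SD of estimate without / with stage |
|---|---|---|---|
| none | 0.1294 / 0.1294 | 1.000 | 0.1303 / 0.1303 |
| 0.3 on level | 0.1301 / 0.1291 | 1.008 | 0.1292 / 0.1292 |
| 0.6 on level | 0.1329 / 0.1296 | 1.026 | 0.1228 / 0.1223 |
| 0.3 on level, 0.3 on change | 0.1373 / 0.1287 | 1.067 | 0.1304 / 0.1296 |
| 0.5 on change only | 0.1409 / 0.1298 | 1.085 | 0.1288 / 0.1288 |

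The baseline covariate absorbs much of a stable stage effect, so the excess is under 3% unless stage also drives the change. The true spread of the estimate hardly moves; the excess sits in the reported standard error.

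**Optional blood draw.** Simulation with 180 randomized in stratified blocks of 4, the same stage mix and random opt-in (block size and opt-in rates assumed). Ratios are without stage ÷ with stage, for R² of 5%, 10% and 15%.

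| Share giving blood | True SD ratio | Reported SE ratio |
|---|---|---|
| All | about 1.00 throughout | 1.026, 1.054, 1.085 |
| Half | 1.010, 1.027, 1.036 | 1.020, 1.047, 1.079 |
| One third | 1.004, 1.021, 1.050 | 1.014, 1.041, 1.071 |

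In a subset some real precision is lost, at most 5.0% here, and in each case less than the formula's figure for the same R². If stage has no effect, adding it costs about 1% at these opt-in rates.

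**The case against.** The strongest reply is that no harm is shown. Nothing in the documents says that stage predicts Treg or MDSC values after treatment, and 11.5 already adjusts for baseline. This stands, and it is why the consequence must be stated conditionally, with zero included in the range. A reader might infer that the standard errors are too large as a matter of fact; the documents do not support that.

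A reader might also turn a 5.4% excess into the loss of about 10% of the donors (1 − 1/1.054²). That does not follow. With stage balanced, the true spread of the estimate is nearly the same with and without stage, so no such share of the information is lost. The error is toward caution and creates no extra false positives.

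Nor do the documents show that the opt-in undoes the randomization. The table in Study-Related Interventions lists the first draw as a pre-study procedure, footnote a places those before registration, and under 4.0 the registrar assigns the arm at registration. On that reading patients opt in before they are allocated. The same footnote separately asks only that blood be drawn before vitamin A starts, so the order is not certain. Either way, exact stage balance among donors is not guaranteed, although the baseline covariate absorbs part of any imbalance.

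Two further replies limit the point without removing it. Under the within-patient reading, adding a stage main effect does nothing. And objective 2.3.1 is descriptive, with no power or decision rule attached, so little depends on this model.

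**Conclusion.** The omission is real: 11.5 does not name the only stratification factor, while the four regression models in 11.3 and 11.4 use stage. For the baseline-adjusted comparison of post-treatment values, the reported standard error is conservative by about 0% if stage adds nothing to baseline, and by 2.6%, 5.4% or 8.5% if it explains 5%, 10% or 15% of the remaining variance. Those shares are assumptions; the documents give no stage effect, standard deviation or number of donors. Some true precision may also be lost because the draw is optional, but less than these figures. Impact is low: the analysis is exploratory and unpowered, and the error is on the cautious side.

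**What to change.** In 11.5, add pre-operative stage (the three strata of 11.2) as a fixed effect in the comparison of post-treatment values adjusted for baseline, or state why it is left out. State that this baseline-adjusted comparison is the one intended, since a stage main effect has no bearing on a purely within-patient contrast. The cost is one phrase and two degrees of freedom. No new data are needed, because stage must already be known to randomize. This aligns 11.5 with 11.3 and 11.4 on stage only; those models also include age and first examine a stage-by-arm interaction, and this point does not require either in 11.5.

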2.3 Exploratory Objectives

- 2.3.1 To describe immunophenotypic changes of monocytes including myeloid derived suppressor cells (MDSCs) in pre- and post-treatment blood samples.

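### Section 11.5 can use the baseline value twice: with only two blood draws, either the baseline covariate adds no precision to time-by-treatment or the time terms are redundant (low priority)

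*Combined protocol and SAP*

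**What the plan says.** Section 11.5 sets one model for T regulatory cells and MDSCs: "These measures will be compared longitudinally between groups using a mixed models approach". Subjects are random, with "time and treatment and time by treatment interaction considered as fixed effects". It closes with: "For these analyses the baseline (pre-treatment) assessment of each outcome will be included as a covariate in the mixed model".

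The sampling scheme has one measurement on each side of treatment. The section headed 5.3 Exploratory Outcomes states: "Peripheral blood samples at 2 time points (before treatment, and after treatment"). The schedule under 5.3 Study-Related Interventions marks the research blood draw pre-study and after vitamin A, with none post-operatively. The draw is optional: "This procedure is only applicable for patients who chose to participate in the research blood draw".

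The status of the analysis is clear. Objective 2.3.1 reads "To describe immunophenotypic changes of monocytes including myeloid derived suppressor cells (MDSCs) in pre- and post-treatment blood samples", and 11.5 opens with "Analyses of changes in lymphocytes will be exploratory in nature". The documents do not say whether the pre-treatment value is an outcome row as well as a covariate. They give no pre-post correlation, SD, test level or expected number of participants for this analysis.

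**The concern.** Adjusting a longitudinal mixed model for baseline is routine when several post-baseline visits form the outcome. Here there is only one such visit, so the listed terms cannot all do useful work.

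- **Reading 1: both samples are outcome rows.** The comparison over time and the time-by-treatment term point this way. The pre-treatment value then stands on both sides of the equation.
- **Reading 2: only the post-treatment sample is an outcome row.** Time is then constant, and there is one row per patient.

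At stake are the precision of the between-arm comparison, the honesty of its standard error under reading 1, and the analyst's freedom to choose between two analyses that the same text supports.

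**Working it through.** The plan states no figure for this analysis, so there is none to reproduce.

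**Inputs.** From the documents: two draws, 1:1 allocation (11.2) and a target of 90 per arm (11.1), taken as an upper bound because the draw is optional. Assumed: pre-treatment SD of 1, post/pre SD ratio s, correlation ρ of 0.3, 0.5 or 0.7, and a two-sided 5% test. Write c = ρs, with n patients per arm.

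**Reading 1, the estimate.** The covariate is constant within a patient, so with complete pairs it cannot alter a within-patient contrast. Time-by-treatment is the difference between arms in mean change, with or without the covariate. In 60 direct REML fits the two agreed to within 5e-15. The true variance is 2(1 + s² − 2c)/n.

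**Reading 1, the subject variance.** Write post = c·baseline + e, with var(e) = s² − c².

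- After adjustment, the between-patient mean square has expectation (s² − c²)/2.
- The within-patient mean square has expectation [(1 − c)² + s² − c²]/2.
- The difference, −(1 − c)²/2, is never positive, so the subject variance is usually estimated at zero.

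**Reading 1, the reported standard error.** With that variance at zero, the fit is ordinary least squares. The baseline slope is 1 in the pre rows and c in the post rows, so the pooled slope is (1 + c)/2. The average residual variance is [(1 − c)²/2 + s² − c²]/2. The interaction involves four cells of n, so its model variance is four times this over n, which is (1 − 2c − c² + 2s²)/n. At s = 1 the ratio of model to true variance is (1 − ρ)(3 + ρ)/[4(1 − ρ)] = (3 + ρ)/4.

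**ANCOVA on the same samples.** Its variance is 2s²(1 − ρ²)/n. At s = 1 this is (1 + ρ)/2 of the change-score variance.

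| s = 1 | ρ = 0.3 | ρ = 0.5 | ρ = 0.7 |
|---|---|---|---|
| True SE, time-by-treatment, n = 90 | 0.1764 | 0.1491 | 0.1155 |
| Reported SE, subject variance zero | 0.1602 | 0.1394 | 0.1111 |
| ANCOVA SE | 0.1422 | 0.1291 | 0.1065 |
| ANCOVA/change variance, (1 + ρ)/2 | 0.65 | 0.75 | 0.85 |
| Excess of true SE over ANCOVA, 1/√[(1 + ρ)/2] − 1 | 24.0% | 15.5% | 8.5% |
| Power of a correctly sized change-score test where ANCOVA has 80%, Φ(2.80√[(1 + ρ)/2] − 1.96) | 62% | 68% | 73% |
| Rejection under the null, 2[1 − Φ(1.96√((3 + ρ)/4))] | 7.5% | 6.7% | 5.9% |

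**Sensitivity to s.** From the closed forms, for s from 0.8 to 1.25 and the same ρ:

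- At s = 0.8, ρ = 0.3 (c = 0.24), the SE ratio is √(1.16/0.5824) = 1.411 and the model/true variance ratio is 1.7424/2.32 = 0.751, so rejection is 8.9%.
- At s = 1.25, ρ = 0.7 (c = 0.875), the SE ratio is √(0.8125/0.7969) = 1.010 and the variance ratio is 1.6094/1.625 = 0.990, so rejection is 5.1%.

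The excess SE therefore runs from 1.0% to 41.1%, and rejection from 5.1% to 8.9%.

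**Simulation of the exact REML fit** (40,000 data sets per setting, no treatment effect):

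- With the subject variance bounded at zero and s = 1, rejection is 7.36%, 6.58% and 6.12% at 90 per arm, and 7.55%, 6.71% and 6.15% at 45 per arm.
- Over all s, ρ and both sizes, the bounded fit rejects 5.12% to 9.17%, a fit allowing negative variance 4.82% to 5.14%, and ANCOVA 4.86% to 5.15%.
- The subject variance is estimated at zero in every run at s = 1 with 90 per arm, but in only 81% (90 per arm) or 63% (45 per arm) at s = 1.25, ρ = 0.7.

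**Incomplete pairs.** With 20% of post samples missing at random, the estimate departs from the complete-pair difference in change by an SD of 12%, 10% or 8% of that estimate's own SD. The equality is then only approximate.

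**Reading 2.** The fixed-effect columns are intercept, time, treatment, time-by-treatment and baseline. Time duplicates the intercept and time-by-treatment duplicates treatment, so the rank is 3 of 5. With one row per patient, the subject effect cannot be separated from residual error. What remains is post-treatment value on arm and baseline: a valid ANCOVA.

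**The case against.** The best counter-argument concerns attribution. The wider standard error and lower power relative to ANCOVA are not caused by the covariate: deleting it leaves the time-by-treatment estimate unchanged, and a difference in mean change is unbiased under randomization. This stands. Those figures measure the precision that the covariate is normally added to gain and here fails to deliver. What double use itself causes is the understated standard error, which is modest, depends on the software's bound at zero and disappears if a negative variance is allowed.

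It also stands that reading 2 is statistically sound, that no error rate is set for 11.5 and so none is breached, and that an exploratory analysis of an optional sample carries little weight.

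A further objection is that ANCOVA yields no within-arm change, although 11.5 also wants changes assessed in each arm. That separate sentence can stay, since only the between-arm model needs replacing. The common-baseline repeated-measures option supplies both.

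None of this gives a reason to keep a covariate that does nothing, or terms that cannot be estimated.

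**Conclusion.** The concern holds, at low priority. The structural result needs no assumed figure: under reading 1 with complete pairs the covariate leaves time-by-treatment unadjusted, and under reading 2 time, time-by-treatment and the subject effect are not identified.

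The sizes are illustrations. They rest on assumed ρ, s and test level, on complete pairs and, for the rejection rates, on a subject variance estimated at zero. At s = 1.25 and ρ = 0.7 both the precision loss and the excess rejection nearly vanish. The algebra is certain; the practical effect depends on the reading, the software and the data. Primary and secondary conclusions are untouched.

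**What to change.** Use baseline once in the between-arm comparison of 11.5, and name one of two models:

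1. ANCOVA of the post-treatment value on arm and baseline value, with the random subject, time and time-by-treatment terms removed.
2. A repeated-measures model with both samples as outcomes, unstructured covariance, a baseline mean common to both arms and no baseline covariate.

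The two differ slightly when a patient has only one sample, so 11.5 should also say how such patients are handled. The within-arm description of change stays. The cost is about one sentence of wording, with the same samples and data, and it is best settled before the marker data are examined.

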11.6 Estimated Accrual Rate

90 patients per year.

Appendix A – Protocol Registration Form

DEMOGRAPHICS

Patient: Last Name: _____ First Name: _____

First Name: _____

MRN: _____ DOB (mm/dd/yy): _____ / _____ / _____

SEX: Male Female

Ethnicity (choose one): Hispanic

□Non-Hispanic

Race (choose all that apply) WHITE BLACK ASIAN

apply): PACIFIC ISLANDER NATIVE AMERICAN
Height: _____ inches Weight: _____ lbs (actual)

Surface Area:

— — (

Principais Discussões

Date of Diagnosis: _____ / _____ / _____

Performance Status: ECOG

PROTOCOL INFORMATION

Date of Registration: / /

MD Name (last) :

Date protocol treatment started: / /

Informed written consent: YES NO

(consent must be signed prior to registration)

Date Consent Signed: _____ / _____ / _____

PID # (to be assigned by WISER):

Protocol Registrar can be contact by calling [contact] between 8:30 AM and 4:00 PM, Monday – Friday.

Completed Eligibility Checklist and Protocol Registration Form must be hand delivered, faxed or e-mailed to the registrar at [name] or [contact].

Appendix B – Subject Eligibility Checklist

IRB Protocol No. _____	CCCW FU Protocol No. 62218
Study Title: A Pilot Study of Neoadjuvant Vitamin A for Resectable Non-Small Cell Lung Cancer	
Principal Investigator: W. [name]	

Inclusion Criteria (as outlined in study protocol)	Criteria is met	Criteria is NOT met	Source Used to Confirm *
Patient must be >18 years of age			
Patients must have biopsy proven or radiographically suspected non-small cell lung cancer.			
Patients must have disease in the chest that is felt to be surgically resectable.			
ECOG performance status of 0-2			
Ability to understand and the willingness to sign an IRB-approved informed consent document			
Exclusion Criteria (as outlined in study protocol)	Criteria NOT present	Criteria is present	Source Used to Confirm *
Patients <18 years of age			
Women who are pregnant or breast feeding.			
Patients may not be receiving any other investigational agents for the treatment of NSCLC			
Patients may not be taking the following medications: high dose vitamin A supplement (multivitamin supplements prohibited only if vitamin A content is greater than 3,500 IU), bexarotene, alitretinoin, tretinoin, adapalene, isotretinoin, acitretin, doxycycline, minocycline or demeclocycline			
Uncontrolled intercurrent illness including, but not limited to ongoing or active infection, symptomatic congestive heart failure, unstable angina pectoris, cardiac arrhythmia, or psychiatric illness/social situations that would limit compliance with study requirements			
Hypervitaminosis A – toxic effects of ingesting too much vitamin A			

This subject is eligible / ineligible for participation in this study.

WISER Assigned PID: _____

Signature of research professional confirming eligibility: _____

Date: _____ / _____ / _____

Signature of Treating Physician: _____

A Pilot Study of Neoadjuvant High Dose Vitamin A for Resectable Non-Small Cell Lung Cancer
Wake Forest Baptist Comprehensive Cancer Center (WFBCCC)
WFBCCC # 62218

Date: ____/____/____

Signature of Principal Investigator**: _____

Date: ____/____/____

* Examples of source documents include clinic note, pathology report, laboratory results, etc. When listing the source, specifically state which document in the medical record was used to assess eligibility. Also include the date on the document. Example: "Pathology report, 01/01/14" or "Clinic note, 01/01/14"

**Principal Investigator signature can be obtained following registration if needed

